3.6 Health Check Phone Call

- On Day 6 of the participant wearing the first sensor as well as on day 6 of participant wearing the second sensor
- Participants will receive a phone call from the study team's mixed methods qualitative Interviewer at a time prearranged when making other appointments
- Participant will be asked a brief series of questions designed to ensure that the participant is experiencing no ill effects from wearing the CGM sensor on their arm
- Interviewer will also ask questions regarding the participant's food log to ensure their understanding as well as to remind them to be documenting honestly
- Participants will be asked to unwrap their copy of Always Hungry? And begin reading chapters 1-5.

3.7 Phase Two, In person Appointment

3.7.1 Measurements

- Participants' Weight and Blood Pressure will be repeated as described In section 3.5 and documented in the participants measurement log.
- An estimated A1c will be obtained from the sensor data retrieved by scanning the sensor using the Abbott Libre Pro reader.

3.7.2 Letter to Primary Care Physician

- If the participants estimated A1C, as indicated on the report from their sensor, is higher than 6.4%, this would indicate that the participant may have progressed to Type 2 Diabetes.
- A letter addressed to the participant's Primary Care Physician will be given to the participant.
- This letter will describe to the physician that the participants estimated A1C fell in to the range of Type 2 Diabetes
- The letter will urge the Primary Care Physician to obtain a blood level A1C to assess the patient's true diabetes status rather than relying on the estimated A1C that we are providing the participant.

3.7.3 Sensor Scanning and Removal

- Using the Abbott Freestyle Libre Pro reader the study coordinator will scan the participants' sensor
- Sensor will then gently be removed from the participant's arm
- The area where the sensor was applied will be wiped down with an alcohol wipe to ensure that the area around the small puncture wound created by the microfilament remains free from any contaminants
- The Reader will be connected to the computer via USB and the sensor data will be uploaded by the Abbott Libre Pro software, Libre View.

3.7.4 Abbott Libre Reports

- A series of reports will be produced by the software based on the information obtained from the participant's sensor data.
- Reports will be labeled solely with the participant's study ID.
- Reports include: Daily Blood Glucose Pattern report, Glucose Pattern Insights report, A Daily Glucose Summary Report, and a Snapshot or 11-day summary report

3.7.5 PowerPoint Presentation

- Participants will be shown a series of slides containing information about the reports that they will receive based on their first sensor reading.
- Instruction about the information they will receive from their second sensor
- Participants will be given basic information about the relationship between carbohydrate intake and blood glucose levels.
- Participants will be taught about the Abbott Libre personal sensor and reader that they will be using during phase 2.
- Discussion and slides regarding the importance of low carbohydrate diet
- Teaching about the difference between simple and complex carbohydrates and which should be included in a healthy low carbohydrate diet and which should be avoided.
- As part of the teaching on low carbohydrate dieting we will discuss the health benefits and side effects that occur when transitioning to a lower carbohydrate diet.

3.7.6 Phase 2 Food Log

- Participants will be asked to complete a daily food log
- Log asks participants to write down the food that they eat and what time they are it.
- Participants are asked to record their food intake in general terms rather than breaking it down in to chloric content, Protein content, or carbohydrate content
- Approximately 2 hours after eating participants will also document their level of hunger and postprandial fatigue
- Participants are asked to document the blood glucose reading that is displayed on their Abbott
 Libre personal reader when they wake up in the morning as well as their last reading before they
 go to bed.
- Participants will also log their blood glucose levels before every meal/snack and then again 2 hours later when they assess their hunger and post-prandial fatigue levels.

3.7.7 Abbott Freestyle Libré personal Sensor and Reader

- Following the PowerPoint presentation and low carbohydrate teaching, participants will have a new sensor applied to the underside of their upper arm on their non-dominate side.
- Sensor number 2 will be applied using the same technique that sensor number one was applied with. This method is outlined in section 3.5.5
- This new sensor will be calibrated to connect to the Abbott Freestyle Libré personal device which will allow participants to receive real time data as well as a glucose reading whenever they use their reader device to scan their sensor.
- Obtaining a reading from the sensor only requires that the reader pass in front of the sensor. This can be done through clothing and never requires a finger stick.
- Participants will be asked to scan their sensor at least once every 8 hours.

3.7.8 Side Effect Log

- Participants will be asked to document and side effects that they experience and when they occur on a side effect log.
- This log will be reviewed so that suggestions can be made about how they could further alter their diet to relieve these side effects.

3.7.9 The CalorieKing: Calorie, Fat, and Carbohydrate Counter (2017):

- All participants will receive a copy of the book, The CalorieKing: Calorie, Fat, and Carbohydrate Counter (2017).
- This book will assist the participants in deciding which foods to eat and which to avoid while eating in such a way as to reduce carbohydrate consumption.

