3.0 Methods

3.1 Study Design: Single arm pilot and feasibility study.

Outcomes;

Primary: Participant Satisfaction	Items on f/u survey and qualitative interview			
Secondary:				
Feasibility	Successful recruitment, Successful sensor wears time			
	20/22 days, Data retrieved from sensor successfully			
Weight Change	Weight at final visit – weight at 2 nd visit			
Knowledge of Low Carbohydrate Eating	Low Carb Knowledge Scale – final - baseline			
Cravings and Hunger	Ratings on food logs			
Intention to continue Low Carbohydrate eating	final survey question			
Side effects of CGM wear, Low Carbohydrate eating	Side effect log			
Utility of CGM feedback for changing diet	Qualitative Interview			

3.2 Study Population and Recruitment:

As identified though MiChart and Data Direct searches, 10-15 adult Michigan Medicine patients who qualify based on inclusion and exclusion criteria will be contacted via US Mail regarding their participation in our study. This letter will explain the study and its requirements and will be accompanied by an opt-out postcard that can be returned if the patient no longer wishes to be contacted. Those who do not return the postcard will be contacted via telephone with further information about the study. Recruiting will also be accomplished through a posting on the UM Health Research website as well as printed materials such as fliers and brochures. Interested and eligible participants will be scheduled to attend a one-on-one in-person baseline visit with the study coordinator at Livonia Health Center.

3.3 Inclusion/Exclusion Criteria:

- 21+ years of age
- A1C 5.7 to 6.4
- No Diabetes medication including Metformin
- BMI >30
- Must speak, read, and write in English
- Must have a phone
- Must have a computer
- Interested in changing diet to improve health
- No current pregnancy
- No previous Bariatric surgery
- Must not classify as either Vegan or Vegetarian
- Must be a patient at the Livonia Health Center

3.4 Informed Consent: At the baseline assessment the Research Coordinator will thoroughly review the Informed Consent document with the participant. If valid informed consent is freely given the baseline data collection will begin.

3.5 Phase One, In-Person Appointment:

- Obtain a valid informed consent
- Baseline measurements including weight, height, and blood pressure

- Power point presentation outlining the study and the participant's role in Phase One.

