- Participants will be given multiple resources to assist them in determining how many carbohydrates are in the foods they consume.
- Participants will be given the book entitled, "The Calorie King, Calories, Fat, and Carbohydrates," which lists the calorie, fat, and carbohydrate content of various foods.
- Possible side effects of low carbohydrate diet will be discussed with the participant and information on how to mitigate the effects of the diet will also be provided.

- Patients will be instructed to fill out a side effect log as well as their diet log during this phase.
- Participants will complete an information sheet, voluntarily suppling their address as well as any information about food allergies they may have.
- Participants will choose two recipes from a group of five options that they would like to make for themselves and/or their immediate family.
- **3.8 Grocery Delivery:** Approximately two days following the participants second visit all of the ingredients for one of their chosen recipes will be delivered to the address provided. All of the ingredients for the second recipe that the participant has chosen will be delivered approximately five days later.
- **3.9 Follow-Up Visit:** Approximately 11 days after the intervention visit:
 - Participants will have the second sensor removed.
 - Data obtained by the sensor will be uploaded and printed out for their review.
 - Participant's data will be compared to their completed food log.
 - Participants will also be provided with a letter to take to their Primary Care Physician (PCP) explaining the study and asking for a prescription for an Abbott Libre personal sensor so that the participant may continue tracking their blood glucose levels following the study.
 - Participants will take the "Completion Survey"
 - Participants will receive either a check or a voucher for \$25.00 for completing the survey and all three of their in-person appointments.
 - Participant wishes to continue wearing a CGM and has found that it has been an effective way to assist them
 in consuming a low carbohydrate diet, they will be given a letter addressed to their Primary Care Physician
 asking for a prescription to continue using the Abbott Libre personal CGM sensors and reader.

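### As described, the side effect log has no daily or 'none' entry and no completeness check, so a blank log is ambiguous and low carbohydrate side effects may be under-counted

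*Protocol*

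**What the plan says.** The outcomes table in Protocol Section 3.1 lists as a secondary outcome "Side effects of CGM wear, Low Carbohydrate eating", and the only source it names is the side effect log.

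The log is introduced at the second visit. Section 3.7 says: "Patients will be instructed to fill out a side effect log as well as their diet log during this phase". Section 3.7.8 describes its content: "Participants will be asked to document and side effects that they experience and when they occur on a side effect log". It then gives the log a use: "This log will be reviewed so that suggestions can be made about how they could further alter their diet to relieve these side effects". The timing of that review is not given, and no daily line, 'none' entry, symptom checklist or check for completeness is mentioned.

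The food log is treated differently. Section 3.7.6 says: "Participants will be asked to complete a daily food log". The detailed Section 3.6 has the caller go over it: "Interviewer will also ask questions regarding the participant's food log to ensure their understanding as well as to remind them to be documenting honestly". Section 3.9 has it compared with the sensor reports at the final visit. Neither place mentions the side effect log.

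Sensor effects have a second route. The detailed Section 3.6 says of the call: "Participant will be asked a brief series of questions designed to ensure that the participant is experiencing no ill effects from wearing the CGM sensor". The calls are placed "On Day 6 of the participant wearing the first sensor as well as on day 6 of participant wearing the second sensor"; the shorter Section 3.6 puts them at about 5 days.

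**The concern.** A record that is written only when something happens does not show whether the participant was recording at all. An empty day, or an empty log, then has two readings: no side effect, or no recording. If the form does not separate them when the data are collected, no rule written later can recover the difference.

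Non-use is plausible. In Phase Two participants also record what and when they eat, hunger and fatigue two hours after eating, and glucose on waking, at bedtime and around every meal or snack (Section 3.7.6). The side effect log is an extra form on top of that, and no planned contact is said to check that it is kept.

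At stake is the tolerability result of a 10-15 person pilot whose data are meant to support a large grant application (Section 1.0). If unkept logs are taken as free of side effects, the error goes one way, toward better tolerability.

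**Working it through.** The protocol states no side-effect rate and no calculation for this outcome, so there is no figure to reproduce. The check compares the text on the two logs and then illustrates the possible size.

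**The two logs in Phase Two, as described**

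| Feature | Food log | Side effect log |
|---|---|---|
| Frequency | Daily (3.7.6) | Not stated; side effects and when they occur (3.7.8) |
| Gone over at the Day 6 call | Yes (3.6) | Not mentioned |
| Gone over at the final visit | Yes, against the sensor reports (3.9) | Not mentioned |
| Other review | – | For diet suggestions, timing not stated (3.7.8) |

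**Inputs for the illustration**

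- Sample size: 10-15 (Abstract; Section 3.2).
- True share of participants with a side effect, p: not given; assumed 30% and 50%.
- Share of participants not keeping the log, q: not given; assumed 10% to 40%.
- Assumed: unkept logs are read as 'none', and not keeping the log is unrelated to having a side effect.

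**Under-count.** Expected observed rate = p × (1 − q); change = −p × q.

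| p | q | Observed | Change (percentage points) |
|---|---|---|---|
| 30% | 10% | 0.30 × 0.90 = 27% | −3 |
| 30% | 20% | 0.30 × 0.80 = 24% | −6 |
| 30% | 40% | 0.30 × 0.60 = 18% | −12 |
| 50% | 10% | 0.50 × 0.90 = 45% | −5 |
| 50% | 20% | 0.50 × 0.80 = 40% | −10 |
| 50% | 40% | 0.50 × 0.60 = 30% | −20 |

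In participants: with n = 15, p = 30% and q = 20%, the expected number with a reported side effect falls from 15 × 0.30 = 4.5 to 4.5 × 0.80 = 3.6. The change is zero if every log is kept, or, under the same independence assumption, if unkept logs can be identified and treated as missing.

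**Zero events.** This is a separate limiting case and does not use the p and q above. With no events among n kept logs, the exact one-sided 95% upper limit is 1 − 0.05^(1/n).

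- n = 12: 1 − 0.05^(1/12) = 22%.
- n = 6: 1 − 0.05^(1/6) = 39%.

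Twelve blank logs would look the same whether all 12 or only 6 had been kept, unless someone asked.

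**What a 'none' entry recovers.** If non-entry is unrelated to side effects, leaving out unkept logs returns the expected rate to p. If it is related, only part is recovered. Take p = 50%, with 30% of affected participants making no entry and every unaffected participant ticking 'none'. Affected participants with an entry are 0.50 × 0.70 = 0.35 of the total, and all with an entry are 0.35 + 0.50 = 0.85. The rate among those with an entry is 0.35 / 0.85 = 41%: better than 35%, but short of 50%.

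**The case against.** The strongest reply is that the defect is inferred from a two-line description. The form is not shown, and one with dated rows or a 'none' box would satisfy the text. Section 3.7 asks for the side effect log alongside the diet log, which is daily, so parallel daily use is compatible with the wording. Section 3.7.8 says the log will be reviewed, and whoever reviews it could ask about a blank. How blanks are counted is a missing-data rule that may sit in a statistical analysis plan not shown here. For the sensor half of the outcome, ill effects are asked about by phone during both wears. Finally, every rate in the illustration is assumed.

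Most of this stands and limits the claim. A reader might infer that the log records events only, that blank logs will be counted as people without side effects, and that the outcome is therefore biased. The documents do not support that: they do not show the form, and they neither state a rule for blanks nor say that the denominator stays at the full 10-15.

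Three things remain. The collection method as written provides no 'none' entry, and an analysis plan cannot restore information that was never collected. The stated review is aimed at relieving side effects that have been written down; it is not described as a check on blanks and has no date. The calls are not named as a source for the outcome, they ask about the sensor only, and the log itself is introduced only for Phase Two, so side effects of the first sensor have no entry in the outcome's one listed source.

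**Conclusion.** The point holds in conditional form. The protocol describes no means of telling a log with nothing to report from a log not kept, although this log is the only listed source for the outcome. If some logs are not kept and blanks are read as 'none', the side effects of low carbohydrate eating will be under-counted, by 3 to 20 percentage points over the assumed ranges. The direction follows from those two conditions; the size rests wholly on assumed rates, and neither condition is stated in the protocol. For effects of sensor wear the point is weaker.

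This is a minor point. It touches one of several secondary outcomes in a small single-arm pilot, and nothing in the protocol is contradictory here. It is worth raising because the remedy is almost free and is not available after data collection.

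**What to change.** In Section 3.7.8, make the Phase Two side effect log daily, with a 'none today' tick beside the space for side effects. In Sections 3.6 and 3.9, add the side effect log to what is checked at the existing Day 6 call for the second sensor and at the final visit. In the outcome definition, report side effects with the number of participants and the number of days with an entry as the denominator, and treat days without an entry as missing. If the form already has such fields, one sentence saying so is enough.

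The cost is a few seconds a day for participants and a smaller denominator. With zero events, for example, the upper limit moves from 25.9% with 10 kept logs to 31.2% with 8, or from 18.1% with 15 to 22.1% with 12. Some bias remains if people with side effects are less likely to make entries, so the number of logs kept should be shown beside the result. No visit or treatment changes.

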3.7.10 Recipes

- Participants will be given 5 recipes that are copied directly from either, "Always Hungry?" By David Ludwig, or Always Delicious by Dawn Ludwig
- Participants will be asked to choose 2 of the recipes that they would like to make for themselves and/or their family.

3.8 Grocery Delivery

- After the participants have chosen two recipes that they would like to try from the five available options, Arrangements will be made to have all of the ingredients for these recipes delivered to the participant's home in two separate deliveries scheduled 5 days apart.
- The Research Coordinator will ask the participant to provide the address that they would like the groceries delivered to, the number of people in their family that the meal will be prepared for, and a list of any food allergies that they or their family members have.

3.9 One-on-one Follow-up Visit

- When Participants arrive for their second appointment they will again have their weight and blood pressure taken as outlined in section 3.5.1.
- The Second sensor will be removed and the reports produced by the sensor will be uploaded and printed out to be gone over with the participant
- The participant's food log will then be compared to the reports produced by the sensor so that some conclusions can be drawn regarding the participant's carbohydrate intake and the reaction of their blood glucose levels.
- The participant will complete one final survey that is designed to be taken within a 10-15 minute period.
- If the participant indicates that they would like to continue wearing the continuous glucose monitor a letter will be sent to their primary care physician requesting a prescription for the patient so that they may obtain one from their pharmacy.
- The participant will be given a check or voucher for their final payment of \$25.00 for completing the study.

3.10 Semi-Structured Qualitative Interview

- After all three in-person visits have been completed
- The Mixed Methods Interviewer will call the participant to discuss the study
- Questions will revolve around the participant's satisfaction with the CGM sensors and the phase-two reader, how their diet was effected by the CGM sensor and information that it gave them, and how they feel about having been diagnosed with pre-diabetes.

3.11 6-Month Follow-up Telephone Interview

- Six months after the participant has completed all three study visits they will receive a telephone call from the studies Mixed Methods Qualitative Interviewer.
- The Interviewer will ask questions about the impact that the study has had on their diet, whether or not they have become diabetic and whether or not they made any effort to obtain their own continuous glucose monitor.
